#### **5.4 Method for Assigning Subjects to Treatment Groups**

Randomization of 1:1 will be assigned at the time of accrual. A randomization schedule will be developed by the study statistician using the method of random permuted blocks. Randomization assignments will be loaded into REDCap and subjects will be randomized by accessing assignments through the REDCap randomization facility.

#### **5.5 Preparation and Administration of Study Drug/Therapy**

Metformin tablets will be provided by the Department of Otorhinolaryngology and will be coordinated through the Thomas Jefferson University Hospital Investigational Drug Service (IDS) Pharmacy. Drug will be stored in locked cabinet until given to the participants. An 8 week supply of metformin will be provided to subjects and the drug will be self-administered by the participants.

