**Description and justification for the route of administration, dosing regimen and treatment period:**

Metformin will be administered orally since this is the route of administration currently approved by the FDA. Beginning one-two weeks prior to planned external beam radiation therapy, the drug will be initiated at a dose of 500mg orally daily for 3 days and will then be increased to 500 mg twice daily. If tolerated, metformin will be further increased to 1000mg twice daily after day 6. Subjects will maintain 1000 mg twice a day dosing until two weeks post radiation.

There are currently multiple studies on-going using doses from between 500 mg twice daily up to 2500 mg per day in the treatment arms. There are also studies using the extended release form for a dose of 1500 mg daily. We have chosen our starting dose and escalation regimen to minimize side effects. The chosen standing dose is based on metformin's therapeutic range (minimal therapeutic dose in diabetic patients is 1500-2000 mg a day). The time of planned exposure to metformin will be 8-10 weeks. We will allow a window of an additional 2 weeks in the event that there are delays in the treatment scheduling but no patients will receive metformin for more than 12 weeks.

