#### **5.6 Subject Compliance Monitoring**

There will be a pill bottle with the appropriate number of metformin tablets distributed to the patients upon enrollment into the trial. The pill bottle will be accompanied with detailed instructions on the proper dosage/number of tablets to take daily as noted above. Upon arrival for post-radiation follow-up, the bottle will be collected by our trial coordinator and the contents will be evaluated for compliance.

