#### **5.8 Packaging**

The study drug will be provided by the Department of Otorhinolaryngology and will be coordinated through the Thomas Jefferson University Hospital Investigational Drug Service (IDS) Pharmacy. The study drug will be packaged in 1 bottle containing 500mg tablets for a maximum of 8 weeks.

The bottle will be labeled “take one tablet daily for three days then one tablet twice daily for three days then two tablets twice daily until two weeks after radiation therapy ends”.

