### 5.12.3 Dispensing of Study Drug

The study drug will be dispensed to the participants in 1 bottle containing 500mg tablets for a maximum of 8 weeks. The bottle will be labeled “take one tablet daily for three days then one tablet twice daily for three days then two tablets twice daily until two weeks after radiation therapy ends” for metformin or bottle will be labeled “take one tablet twice daily until two weeks after radiation therapy ends”. The amount of pills dispensed to every participant will be logged in the accountability logs by the pharmacist. The participant will be instructed to bring the bottle and all the pills that were not taken the day of the visit two weeks after the completion of radiation. Regular study drug reconciliation will be performed only at the end of the study.

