### **6.1 Study Visit Schedule**

Screening: Trial Coordinator will screen the office charts for possible inclusion in the trial. Labs for the screening part will be available from pre-admission testing that is standard of care.

Visit 1: Subjects that meet the inclusion criteria after reviewing the initial biopsy, laboratory data and clinical chart will be approached the day of their follow up after initial biopsy. The study coordinator will meet with the prospective candidates and go over the protocol, answer questions and obtain informed consent. If the subject is agreeable to the study, a physical exam will be performed, blood and saliva will be collected, and participant will be randomized.

Metformin/placebo Instructions on how to take study drug will be given and times for follow up phone calls for tolerability and safety will be arranged with participants. Participants will be instructed to call with any side effects or adverse events that occur in the interim of the follow up phone calls. The exact date to start the metformin will be determined this visit based on the planned start of radiation. Subject will be instructed to start taking the metformin/placebo at any point from 1 to 7 days from the start of radiation.

Quality of life measures including the EORTC QLQ – H&N35, mucositis score, Multidimensional fatigue inventory and the Xerostomia Questionnaire (XQ) will be administered on an iPad through the website ([https://az1.qualtrics.com/jfe6/preview/SV\\_87y9lyJ0sFo8oJv](https://az1.qualtrics.com/jfe6/preview/SV_87y9lyJ0sFo8oJv)). Patients will be identified only by an ID number.

Visit 2: Subjects will come in during the 3rd week of their radiation for blood draw, saliva collection, physical exam, quality of life questionnaires and tolerability assessment. An inventory of medication will also be taken to assess compliance. Location of radiation is not dictated by this protocol.

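### One 8-week bottle with no described refill covers only the low end of the planned 8–10 weeks of metformin; separately, section 5.3 restarts drug after Grade 3 toxicity at grade 2, where 1.6 and 6.3 require grade 1 or lower

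*Combined protocol and SAP*

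**What the plan says.** **Supply.** Section 5.5: "An 8 week supply of metformin will be provided to subjects and the drug will be self-administered by the participants". Section 5.8: "The study drug will be packaged in 1 bottle containing 500mg tablets for a maximum of 8 weeks". Section 5.12.3 repeats it: "The study drug will be dispensed to the participants in 1 bottle containing 500mg tablets for a maximum of 8 weeks". Section 5.6 fixes the timing: "There will be a pill bottle with the appropriate number of metformin tablets distributed to the patients upon enrollment into the trial". The bottle comes back at the post-radiation visit. At Visit 2, in the third week of radiation, section 6.1 adds "An inventory of medication will also be taken to assess compliance", and says nothing about resupply.

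**Planned dosing.** Section 1.6: "The time of planned exposure to metformin will be 8-10 weeks". It continues: "We will allow a window of an additional 2 weeks in the event that there are delays in the treatment scheduling", with the limit that "no patients will receive metformin for more than 12 weeks". Section 5.2 and the bottle label continue dosing until two weeks after radiation. The label gives one 500 mg tablet a day for three days, two a day for three days, then four a day.

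**Restart after Grade 3 toxicity judged probably or definitely drug related.** Section 5.3 gives half dose once the toxicity has come down to grade 2. Section 1.6 gives half dose only at grade 1 or lower and stops for good if the toxicity has not resolved after 3 days. Section 6.3 also requires grade 1 or lower and otherwise stops for good, with no day limit.

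**The concern.** The dispensing instruction and the dosing plan do not match. A patient on a longer course who takes every labelled dose runs out before the intended stop, and so before the blood and saliva collected at Visit 3, two weeks after radiation. Section 7.1 bases the primary contrast on change from baseline to post-treatment. It does not name the post-treatment visit, so how far an early run-out would affect that contrast cannot be worked out from the documents. The compliance check could also miss the problem: a patient who ran out early returns an empty bottle, which looks like full compliance.

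The Grade 3 conflict is a separate safety matter. A patient improved only to grade 2 is put back on drug under 5.3 and kept off it under 1.6 and 6.3, so the action taken depends on which section the site reads.

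**Working it through.** **Inputs.** Tablet schedule: label in 5.8 and 5.12.3. Supply: 8 weeks = 56 days. Planned dosing: 56–70 days, ceiling 84 (1.6). Dosing after radiation: 14 days. Lead-in: 7–14 days (1.6) or 1–7 days (6.1, read as before radiation). The documents give neither a tablet count nor the length of radiation.

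**The plan's own range.** Exposure = lead-in + radiation + 2 weeks. With 1.6's lead-in, 1 + 5 + 2 = 8 weeks and 2 + 6 + 2 = 10 weeks, so the stated 8–10 weeks fits radiation of 5–6 weeks, although other combinations also give it.

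**Tablets needed on the label.** 3×1 + 3×2 + 4×(days − 6):

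- 56 days: 9 + 200 = 209
- 70 days: 9 + 256 = 265 (56 more, or 14 days at four a day)
- 84 days: 9 + 312 = 321 (112 more, or 28 days)

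**How long one bottle lasts.** With *a* days at one tablet and *b* days at two, days covered = a + b + (fill − a − 2b)/4. Two fills are tried: 209 (exactly 8 weeks on the label) and 224 (4 × 56, an assumption). Two titrations are tried: 3+3 (the label) and 5+5 (the slowest, using the 2-day allowance that 5.3 gives on both steps).

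| Fill | Titration | Days covered | Gap at 56 d | Gap at 70 d | Gap at 84 d |
|---|---|---|---|---|---|
| 209 | 3+3 | 56.0 | 0 | 14.0 | 28.0 |
| 209 | 5+5 | 10 + 194/4 = 58.5 | 0 | 11.5 | 25.5 |
| 224 | 3+3 | 6 + 215/4 = 59.75 | 0 | 10.25 | 24.25 |
| 224 | 5+5 | 10 + 209/4 = 62.25 | 0 | 7.75 | 21.75 |

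Section 5.2 and the study summary put full dose after day 6 (+2), about 8 days of titration. Taken as 5+3, that gives 8 + (209 − 11)/4 = 57.5 or 8 + (224 − 11)/4 = 61.25 days, inside the range above. Placebo at two a day needs 112, 140 and 168 for 56, 70 and 84 days, so a 56-day placebo bottle runs out 14 and 28 days early at 70 and 84 days.

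**Longest radiation course covered.** Days covered − 14 − lead-in:

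- Section 1.6 start: 56 − 14 − 14 = 28 up to 62.25 − 14 − 7 = 41.25 days
- Section 6.1 start: 56 − 14 − 7 = 35 up to 62.25 − 14 − 1 = 47.25 days

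**Gap by assumed radiation length.**

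| Radiation | 1.6 start: dosing days | Gap (days) | 6.1 start: dosing days | Gap (days) |
|---|---|---|---|---|
| 35 d | 56–63 | 0–7 | 50–56 | 0 |
| 42 d | 63–70 | 0.75–14 | 57–63 | 0–7 |
| 49 d | 70–77 | 7.75–21 | 64–70 | 1.75–14 |

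Dosing beyond 70 days uses 1.6's contingency window.

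**Grade 3 restart.** Take a patient on 2000 mg/day whose toxicity falls from grade 3 to grade 2. Under 5.3 the patient resumes 1000 mg/day; under 1.6 and 6.3 no drug is given. Section 5.3's own Grade 2 rule stops drug if symptoms have not resolved within 3 days. If that rule applies after the restart, the extra exposure is at most 3 × 1000 mg = 3 g, or 6 tablets. If it is not read that way, 5.3 sets no limit.

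**The case against.** Nothing in the protocol forbids a refill. Section 5.6 speaks of an appropriate number of tablets, 1.6 and 5.3 schedule weekly calls, Visit 2 takes an inventory, and tablets are logged and reconciled, so a patient running low might well be noticed. Dose holds, reductions and missed doses all stretch the bottle. With 6.1's shorter lead-in there is no gap at 5 weeks of radiation and at most 7 days at 6. On the numbers, the label's titration is 3+3, so the 5+5 rows are not label dosing; the 224 fill is assumed; and the 21-day gap needs 77 days of dosing, which is contingency time.

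Those points about the numbers are fair, and the working marks them. Slower titration and a larger fill only shorten the gap, however, and no combination tried reaches 70 days at full dose. The calls and inventory assess tolerability and compliance; none is a stated resupply, and 5.8 and 5.12.3 cap the bottle at 8 weeks. Appendix A marks study drug at Visits 1 and 2, but gives radiation the same marks, so these show ongoing treatment.

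On Grade 3, 6.3 is the dedicated dose-modification section and agrees with 1.6, 5.3's Grade 2 rule arguably limits the exposure, 2.5 holds metformin for any grade 3 or 4 SAE, and 8.4 allows discontinuation at the physician's discretion. These reduce the risk but leave the restart grade unsettled. It is also true that the two problems are unrelated and need separate edits.

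**Conclusion.** Both points hold. The supply is 56 days against up to 70 planned and 84 allowed. At full dose the shortfall is about 8–14 days at 10 weeks and 22–28 days at 12, with none at 8 weeks. That much rests on the label schedule, the two fills and the titration range. The gaps by radiation length also rest on assumed courses of 5–7 weeks. No bias in the primary contrast is claimed or quantified, and the power figures are unaffected.

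The Grade 3 sections give opposite instructions for a patient at grade 2. On the reading that limits it, the excess exposure is small (3 g over 3 days), but a drug-restart rule should not depend on the section consulted. Both should be fixed.

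**What to change.** - **Supply (5.5, 5.8, 5.12.3).** Dispense at the start, or refill at Visit 2, enough to reach two weeks after radiation: 265 metformin tablets for 10 weeks and up to 321 for 12; 140 and 168 for placebo. Record the last-dose date at Visit 3, so that an early run-out can be told from full compliance.
- **Grade 3 rule.** Change 5.3 to restart at half dose only at grade 1 or lower, with permanent discontinuation otherwise. Use one time limit in 1.6, 5.3 and 6.3; 1.6's 3 days is the only one stated. Align the Grade 2 limit at the same time, since 5.3 and 6.3 give 3 days and 1.6 gives none.
- **Clean-up.** Delete the instruction in 5.3 that ends dosing on the eve of surgery, which does not fit the post-radiation stop. State one start window in 1.6 and 6.1.

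Cost: one protocol amendment, and a larger fill or one refill of a generic tablet and placebo at an existing visit. No added visits.

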#### **5.6 Subject Compliance Monitoring**

There will be a pill bottle with the appropriate number of metformin tablets distributed to the patients upon enrollment into the trial. The pill bottle will be accompanied with detailed instructions on the proper dosage/number of tablets to take daily as noted above. Upon arrival for post-radiation follow-up, the bottle will be collected by our trial coordinator and the contents will be evaluated for compliance.

#### **5.7 Prior and Concomitant Therapy**

All medications are permitted except those that are contraindicated with metformin under current FDA recommendations. It is important to note that the medications that are contraindicated with metformin are contraindicated due to concern for theoretical interactions. See section 4.2 for more information.

#### **5.8 Packaging**

The study drug will be provided by the Department of Otorhinolaryngology and will be coordinated through the Thomas Jefferson University Hospital Investigational Drug Service (IDS) Pharmacy. The study drug will be packaged in 1 bottle containing 500mg tablets for a maximum of 8 weeks.

The bottle will be labeled “take one tablet daily for three days then one tablet twice daily for three days then two tablets twice daily until two weeks after radiation therapy ends”.

#### **5.9 Blinding of Study Drug**

The bottle will be non-descript and contain either metformin or placebo depending on randomization. Patients will be blinded to which pill (metformin or placebo) they will receive. Pill distribution will be completed by the pharmacist who will not be blinded. Principal Investigator and care providers making assessments will not be blinded.

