### **2.1 Primary Objective:**

We have chosen a cytokine/chemokine profile analysis as a surrogate marker of trending inflammatory reaction. This response drives the severity of mucositis/xerostomia and acute radiation toxicity. The blood and saliva counts will be compared in the pre-treatment sample, during treatment samples and post treatment samples. Luminex technology with 40 cytokines markers will be used (Luminex technology with the Milliplex MAP Human Cytokine/chemokine Magnetic kit I (41 analytes) (sCD40L, EGF, Eotaxin, FGF-2, Flt-3 ligand, Fractalkine, G-CSF, GM-CSF, GRO, IFN- $\alpha$ 2, IFN- $\gamma$ , IL-1 $\alpha$ , IL-1 $\beta$ , IL-1ra, IL-2, IL-3, IL-4, IL-5, IL-6, IL-7, IL-8, IL-9, IL-10, IL-12 (p40), IL-12 (p70), IL-13, IL-15, IL-17A, IP-10, MCP-1, MCP-3, MDC (CCL22), MIP-1 $\alpha$ , MIP-1 $\beta$ , PDGF-AA, PDGF-AB/BB, RANTES, TGF- $\alpha$ , TNF- $\alpha$ , TNF- $\beta$ , VEGF). Blood and saliva samples will be drawn before, during and immediately after treatment and every three months thereafter for one year. All blood samples will be taken by a phlebotomist who will be blinded as to whether the patient is in the experimental (radiation + metformin) or control (radiation + placebo) groups.

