### **2.2 Secondary Objective:**

- Assess safety and tolerability of metformin treatment in subjects undergoing external beam radiation treatment for head and neck cancer.

- To determine the effect of metformin treatment on symptoms of **xerostomia** as assessed by the Xerostomia Questionnaire (XQ)
- To determine the effect of metformin treatment on symptoms of **mucositis** as assessed by WHO classification
- To determine the effect of metformin treatment on symptoms of **dysphagia** as assessed by the MD Anderson Dysphagia Inventory
- To determine the effect of metformin treatment on symptoms of **Fatigue** as assessed by the Multidimensional fatigue inventory (MFI).

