#### **5.2 Treatment Regimen**

Metformin is the therapeutic agent in the protocol. The initial starting dose will be 500mg orally daily for 3 (+2 days) days which then will be increased to 500 mg twice daily and, if tolerated, further increased to 1000mg twice daily after day 6 (+ 2 days). Patients will maintain 1000 mg twice a day dosing until 2 weeks after completing their radiation. This dose schedule has been shown to be well tolerated.

The placebo will be dosed as 1 tab BID and will not have a dose escalation.

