**Rules for dose modification: Toxicity monitoring, dose modification and treatment of complications:**

Particular attention will be paid in the first three days of treatment. Patients will take 500mg/day for 3 days (+2 days). From day 4, 500mg twice daily and then in 3 days (+2 days) dose escalation to 1000mg twice daily will be achieved. This will be taken until the day before surgery after dinner. A phone call on the day of each dose escalation will be made in order to evaluate the tolerability of the drug and also weekly thereafter. Patients will be instructed to contact the clinical investigators should any toxicity occur during the study.

Metformin will not be started if CT scan with intravenous contrast is scheduled. After the scan they will be instructed to start the metformin the following day. This approach is more stringent than the most recent recommendation of the American College of Radiology which does not recommend holding metformin in the absence of comorbidities (renal insufficiency, liver dysfunction, alcohol abuse, cardiac failure, myocardial or peripheral muscle ischemia, sepsis or severe infection) which are exclusion criteria for this clinical trial.

Toxicity will be evaluated using the most recent version (version 3) of the NCI toxicity criteria, i.e. the NCI Common Terminology Criteria for Adverse Events (CTCAE) version 4.0. The CTCAE provides descriptive terminology and a grading scale for each adverse event listed. A copy of the CTCAE can be found at <http://ctep.cancer.gov>.

Grade 1 toxicity: Patient will be maintained on full dose.

Grade 2 toxicity: Dose will be reduced by 50% until grade 1 or lower. If symptoms are not resolved within 3 days the treatment will be discontinued definitively.

Grade 3 toxicity (probably or definitely drug related): Treatment will be interrupted and toxicity reassessed daily. If toxicity improves to grade 2, dose will be reduced by 50%.

Grade 4 toxicity (probably or definitely drug related): Treatment will be discontinued definitively.

In case of grade 1 or 2 diarrhea (the most frequent side effect) a concomitant administration of loperamide will be provided.

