## **6.3 Dose Delays and Dose Modifications**

Toxicity will be evaluated using the most recent version (version 4) of the NCI toxicity criteria, i.e. the NCI Common Terminology Criteria for Adverse Events (CTCAE) version 4.0. The CTCAE provides descriptive terminology and a grading scale for each adverse event listed. A copy of the CTCAE can be found at <http://ctep.cancer.gov>.

Grade 1 toxicity: Patient will be maintained on full dose.

Grade 2 toxicity: Dose will be reduced by 50% until grade 1 or lower. If symptoms are not resolved within 3 days of toxicity development the treatment will be interrupted definitively.

Grade 3 toxicity (probably or definitely drug related): Treatment will be interrupted. Toxicity will be evaluated daily and if toxicity improves to grade 1 or lower dose will be reduced by 50%. If toxicity is not improved or resolved or reduced to grade 1, treatment will be interrupted definitively.

Grade 4 toxicity (probably or definitely drug related): Treatment will be permanently discontinued.

In case of grade 1 or 2 diarrhea (the most frequent side effect) a concomitant administration of loperamide will be provided.

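### Section 5.9 leaves the assessing clinicians unblinded without a stated reason, and escalation-day calls have no placebo counterpart, so clinician-judged outcomes are at risk of bias of unknown size and direction

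*Combined protocol and SAP*

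**What the plan says.** Section 5.9 sets out who is blinded. For patients: "Patients will be blinded to which pill (metformin or placebo) they will receive". An unblinded pharmacist distributes the pills. For everyone who assesses outcomes: "Principal Investigator and care providers making assessments will not be blinded". No section gives a reason, and section 8.3 (unblinding) speaks only of subjects. Section 2.1, in contrast, protects the sampling step: "All blood samples will be taken by a phlebotomist who will be blinded".

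Safety and tolerability is the first secondary objective in section 2.2, and mucositis is to be "as assessed by WHO classification". Under section 8.2 the investigator asks about, and where appropriate examines for, adverse events at every contact. Attribution to drug then drives action. Section 6.3 reads "Grade 3 toxicity (probably or definitely drug related): Treatment will be interrupted", and sections 1.6 and 5.3 put the same condition on grade 3 and grade 4 toxicity.

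On contact with patients, sections 1.6 and 5.3 both state: "A phone call on the day of each dose escalation will be made in order to evaluate the tolerability of the drug", with weekly calls after that. Section 5.2 states: "The placebo will be dosed as 1 tab BID and will not have a dose escalation". Section 6.1 (Visit 1) has tolerability and safety calls arranged with participants, without distinguishing the arms.

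**The concern.** The plan blinds the person who draws blood for a Luminex assay, a task that needs little judgement. It does not blind the people whose judgement is itself the measurement. An assessor who knows that a patient takes placebo has little reason to attribute an event to the drug. An assessor who hopes for radioprotection may, without intending it, grade mucositis lower on metformin.

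The call schedule adds a separate problem. Patients who are asked about symptoms more often tend to report more of them. If only one arm is called on escalation days, event counts in the first week are not collected alike.

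At stake are the safety and tolerability objective and, depending on who rates it, the mucositis comparison. Neither problem can be repaired once the data are collected.

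**Working it through.** **1. The plan's own figures.** No stated figure rests on assessor blinding, so the check here is that changing it leaves the design intact. The exosome figure in section 7.4 reproduces: a two-sided t-test at alpha 0.05 with 25 per arm has power 0.801 at 0.81 SD. The single-test alphas in the cytokine table also reproduce. For K = 5 of 40, 5 × 0.8 × 0.05 / (35 × 0.95) = 0.0060. These depend on the number per arm, the error rate and the effect size. Blinding the graders alters none of them.

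**2. Where knowledge of arm can enter.**
- *Elicitation and grading of adverse events:* done by the investigator (8.2), who is unblinded (5.9). Exposed.
- *Attribution to study drug:* a condition for the grade 3 and 4 actions in 1.6, 5.3 and 6.3. In the section 8.5.1 table it also changes the reporting timeline, for example for unexpected grade 3 events without hospitalization. Exposed.
- *Mucositis:* section 2.2 specifies the WHO classification. Section 6.1 and Appendix A (note D) list a mucositis score among the questionnaires given on an iPad. No section names the rater. Exposed only if a clinician assigns the grade.
- *Xerostomia, dysphagia, fatigue:* patient questionnaires (2.2), although section 3.1 also has them assessed at follow-up by medical-record review. Exposed only as far as records written by unblinded clinicians are used.
- *Cytokines and exosomes:* laboratory assays (2.3), with blood drawn by a blinded phlebotomist (2.1). Not shown to be exposed.

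**3. Call schedule.** Metformin has two escalation steps, from 500 mg daily to 500 mg twice daily and then to 1000 mg twice daily. The rule in 1.6 and 5.3 therefore generates two escalation-day calls per metformin patient. Placebo has no steps, so the rule generates none. The weekly calls are timed from the escalation calls, which leaves their start undefined for placebo. Section 6.1 provides for calls in both arms but does not place them on matching days.

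**4. Possible size (assumption only).** Suppose there is no true effect and clinicians grade mucositis. Let p be the severe rate in both arms, using the 67% and 69% cited in section 1.2. Let x be the share of severe cases recorded as non-severe in the metformin arm only. The false difference is p − p(1 − x) = p·x.

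| x | p = 0.67 | p = 0.69 | Two-sided Fisher test, 25 per arm: chance of p-value < 0.05 |
|---|---|---|---|
| 0 | 0 | 0 | 2.3–2.5% |
| 0.1 | 0.067 | 0.069 | about 5% |
| 0.2 | 0.134 | 0.138 | 11–12% |
| 0.3 | 0.201 | 0.207 | 24–25% |

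At x = 0.2 and p = 0.67 this is 0.134 × 25 = 3.35 patients. The standard error of the difference with no true effect is √(2 × 0.67 × 0.33 / 25) = 0.133, so a shift of this size would be about one standard error.

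Three limits apply. No document supports any value of x. A grade 4 case scored one grade lower is still severe, so x counts only cases that cross the threshold. The 67% and 69% come from patients on radiation plus cisplatin, whereas this trial does not require chemotherapy.

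**The case against.** The strongest reply is that the consequence is limited. This is a pilot feasibility trial with laboratory primary endpoints. Three of the four symptom outcomes use patient questionnaires. Section 7.2 is primarily descriptive and specifies no between-arm comparison of drug-related events. All of this is true, and it rules out any claim that the main result is compromised. It does not remove the point: an arm summary distorted by the observer stays distorted without a p-value, and safety is the first secondary objective.

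A second reply is that simply not telling assessors the allocation would not blind them. Metformin comes as tablets with a step-up label and placebo as capsules labelled one twice daily (5.8, 5.11, 5.12.3). Staff give dosing instructions, take a medication inventory and reconcile bottles (5.6, 6.1). This stands, and the fix has to separate product handling from grading.

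A third is that investigators must apply drug-specific rules. The documents do not say that this requires the allocation. If the sponsor thinks it does, the protocol should say so.

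Some stronger readings are tempting but not supported:
- *Placebo patients are not called.* Section 6.1 arranges calls without distinction of arm, and no section excludes placebo patients.
- *Unblinded investigators grade mucositis.* The rater is not named.
- *The outcomes are biased in metformin's favour.* Only exposure to bias is shown. Hopeful grading would flatter metformin, while extra calls and readier attribution would count against it.
- *Open assessment brings no benefit.* The documents are silent on the reason, which is not the same thing.

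**Conclusion.** The point holds as a risk of bias. Adverse-event elicitation, CTCAE grading and attribution are made with knowledge of arm and without a stated reason. The WHO mucositis grade shares that exposure if a clinician assigns it. As written, the call rule can also produce unequal ascertainment, by up to two calls per patient in about the first week.

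Size and direction are unknown. A reader might take the 13-point row of the table as an expected effect. It is one value in an assumed range of about 7 to 21 points, and it depends on an undocumented misgrading rate, a clinician rater and a severe-mucositis rate from a different treatment population. A reader might also extend the point to the cytokine and exosome results, which the documents do not support. The change is worth making because it is cheap and cannot be made after the fact, but the primary analysis does not depend on it.

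**What to change.** 1. **Section 5.9.** Replace the sentence on assessors with text such as: *Allocation is known only to the investigational pharmacist and the study statistician. Staff who grade adverse events or mucositis, or who decide attribution to study drug, are not given the allocation. Emergency unblinding is through the pharmacy.* Restrict access to REDCap assignments (5.4) in the same way.
2. **Sections 5.6 and 6.1.** Because the products and labels differ visibly, assign dosing instructions, pill counts, the Visit 2 inventory and bottle reconciliation to the pharmacist or other existing staff who do not grade outcomes. Patients may still reveal their regimen, so this reduces observer bias but does not guarantee a blind.
3. **Sections 1.6, 5.3 and 6.1.** Make tolerability calls on the same calendar days in both arms with the same script, then weekly in both.
4. **Sections 2.2 and 6.1 and Appendix A (note D).** Reconcile these on who scores mucositis and with which instrument.
5. **Any assessor who must stay unblinded.** State the reason, and report the clinician-graded outcomes as open-label assessments.

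The cost is protocol wording, a REDCap permission setting, up to two extra short calls per placebo patient (at most 2 × 25 = 50 calls), some reassignment of pill handling, and emergency unblinding through the pharmacy. Sample size and stated power are unchanged, and no additional reader is needed.
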